7.2.2 Serious adverse events (SAEs)

A serious adverse event is any untoward medical occurrence or effect that:

- results in death;
- is life threatening (at the time of the event);
- requires hospitalisation or prolongation of existing inpatients' hospitalisation;
- results in persistent or significant disability or incapacity;
- is a congenital anomaly or birth defect; or
- any other important medical event that did not result in any of the outcomes listed above due to medical or surgical intervention but could have been based upon appropriate judgement by the investigator.

An elective hospital admission will not be considered as a serious adverse event.

Only SAEs occurring during or directly after the use of the BiaB-box will be considered and reported as SAEs.

The investigator will report all SAEs to the National coordinator without undue delay after obtaining knowledge of the events, except for the following SAEs:

• Events related to the indication of the HCP consultation and not related to the procedures performed with the BiaB-box, as interpreted by the HCP.

The National coordinator will report the SAEs through the national applicable way to the accredited IRB that approved the protocol, within 7 days of first knowledge for SAEs that result in death or are life threatening followed by a period of maximum of 8 days to complete the initial preliminary report. All other SAEs will be reported in line listings after study closure.

8. STATISTICAL ANALYSIS

The formal statistical analysis plan will be finalized prior to database lock, and it will include a more technical and detailed description of the planned statistical analyses. This section is a summary of the planned statistical analyses of the most important endpoints including primary and key secondary endpoints.

8.1 Primary study parameter

8.1.1 Statistical hypothesis

Use of BiaB reduces time to diagnosis as compared to usual care.

8.1.2 General considerations

To demonstrate whether BiaB use shortens time to diagnosis as compared to usual care, the time from presentation with breathlessness to diagnosis for breathlessness will be compared between the usual care group and the BiaB intervention group.

Time between presentation and diagnosis will be summarised as number of days (median with interquartile range) for patients in the usual care group and BiaB intervention group.

Additionally, analyses will be performed stratified per country and will be presented for the different study populations. The stepped-wedge study design, including potential clustering effects, will be considered in the analysis.

8.2 Secondary study parameter(s)

8.2.1 Statistical hypothesis

Use of BiaB increases the amount of new COPD and/or heart disease diagnoses as compared to usual care.

8.2.2 General considerations

All secondary analyses will be stratified per country and results will be presented for the different study populations. All results will be compared between the usual care group versus the BiaB intervention group. Data will be summarised as descriptive statistics (number of observations, mean, SD, median, interquartile range, minimum and maximum) where appropriate. The stepped-wedge study design, including potential clustering effects, will be considered in the analysis.

- To evaluate the number of newly diagnosed patients with COPD and/or heart disease
 (CVD) in patients with breathlessness, the following outcomes will be reported: frequency
 and cumulative incidence of new (working) diagnosis of COPD and/or heart disease.
- To demonstrate usability and efficiency of BiaB the following statistics will be reported:
 - Frequency of use of: BiaB, Lung function tests, ECG measurements,
 - The distribution of working diagnosis outcomes from the BiaB box,
 - Frequency of: Referral to specialist (and type), Acute hospital admission, Emergency room visits,
 - Clinical outcomes; BiaB report and advice, patient characteristics,
 And:
 - Economic analysis will be performed; reporting either cost-benefit or budget impact.

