A recent literature review on incorporating clinical tools into a clinical decision support system for primary care, aimed at efficiently and accurately diagnosing chronic dyspnea, suggested a staged approach to testing. Initially, after history taking and physical examination, simple tests such as spirometry, pulse oximetry (SpO₂), and electrocardiography (ECG) should be performed.⁵ If the diagnosis remains uncertain, the next step involves additional tests, including chest X-ray, full blood count, thyroid function tests, and N-terminal pro-B-type Natriuretic Peptide (NT-proBNP test). Patients who remain undiagnosed are then referred for advanced testing, such as thoracic CT scans or echocardiograms (Figure 2).3⁵

[figure not shown]

Figure 2. A summary of the stepwise approach for dyspnea assessment and the probability of elucidating the causal diagnosis based on included studies of the literature review of Sunjaya et al.⁵

Although the tests from the stepwise approach by Sunjaya et al. are available in many settings, the process of ordering, performing, and acquiring results often requires multiple appointments at different locations, leading to diagnostic delays. There is currently a lack of quick and easy tests for HCPs to diagnose the cause of breathlessness. Therefore, we have developed "Breathlessness diagnostics in a Box (BiaB)", an easy and reliable tool intended to support HCPs with fast execution of diagnostic procedures required to identify the underlying cause of breathlessness (Figure 3).

[figure not shown]

Figure 31. Content of the BiaB box

The BiaB-box includes the following devices: an iPad, an Oscillometer (the Ambulatory Lung Diagnosis System (ALDS)), an ECG, a point-of-care device to test D-dimer and NT-proBNP tests, and an SpO₂ meter. The BiaB-application (BiaB-app) guides the HCP through the necessary steps for conducting tests and collecting essential data, such as clinical history, questionnaires. The BiaB-app is also a platform of other applications (ALDS, ECG, ECG overread, Castor eCRF, point-of-Care), facilitating the interpretation and integration of the results of the tests that are included in BiaB. Upon completion of the BiaB steps, the application provides a report for the HCP as a guidance for the diagnosis in patients with breathlessness, based on the BiaB decision tree (section 5.1.7).

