5.1.1 Oscillometry

Oscillometry is a non-invasive technique for assessing lung function, as it requires only 45-60 seconds of tidal breathing to measure the mechanical properties of the respiratory system. This makes the measurement suitable for patients of all ages and with severe respiratory conditions. It also reduces the number of errors as compared to other methods (e.g., spirometry).

Oscillometry can be used to evaluate airway resistance, reactance, and compliance, insights that are challenging to obtain with other methods. This quality makes oscillometry especially sensitive for obstructive diseases like asthma and COPD, and correlations with physiological small airways dysfunction have also been shown. 14–16

The Ambulatory Lung Diagnosis System (ALDS), manufactured by Lothar Medtec, can be used to perform oscillometry and spirometry (Figure 5). The ALDS follows the European Respiratory Society (ERS) technical standards for measurement and reporting of oscillometry.

[figure not shown]

Figure 53. Oscillometry and spirometry performed with the ALDS system. A) Schematic overview of oscillometry process and decision support by the ALDS. B) Example of a report generated by the ALDS.

The measurement is performed using approximately 45-60 seconds of tidal breathing. Three measurements of 15 seconds will be performed, during which the patient will calmly breathe in and out while wearing a nose clip. This requires no specific training or effort from patients. The HCP can be trained within 15 minutes on how to perform the measurement and the requirements for accurate measurement. The ALDS has built-in quality control measures and provides feedback if quality is not sufficient.

Contingent on the results of the oscillometry testing, reversibility testing can also be conducted using the ALDS device, in addition to standard oscillometry measurements. When the ALDS suggests execution of a reversibility test, this is performed according to the ERS guideline with use of 400 μ g Salbutamol as the bronchodilator. ¹⁷ If required, post-bronchodilator spirometry can also be performed using the ALDS device after training of HCPs.

The BiaB-app and the ALDS are integrated seamlessly. The complete ALDS output will be integrated in the BiaB-report. The resulting physiological interpretation, combined with the clinical BiaB-decision tree interpretation will be presented in the BiaB-report.

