6.1.2 Secondary study endpoints

6.1.2.1 First secondary endpoint

The first secondary endpoint is the number of new diagnoses of COPD and heart disease (CVD) in patients (usual care group versus BiaB intervention group).

Required variables:

- The number of newly diagnosed patients
- The number of new diagnoses
- The number of diagnoses per patient
- The number of patients presenting with breathlessness
- The type of diagnosis

Strategy: Data will be retrieved periodically (up to 12 months, to account for referral waiting times) from HCP reported outcomes (date and type of diagnosis). All types of diagnosis will be recorded. For determining the secondary endpoint, type of diagnosis will be categorized as either heart, respiratory, psychological, and other. In case no diagnosis is reported, this will be reported as late diagnosis. If multiple diagnoses are recorded, all will count towards the endpoint. In countries where a preliminary diagnosis is entered int the medical records to make prescription of medication possible before diagnostic tests are performed, the date of diagnosis will be validated by the HCP to ensure final clinical diagnosis date.

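### Sections 6.1.2.1 and 8.2.2 disagree on whether working diagnoses count in the first secondary endpoint, and counting them can inflate the BiaB count

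*Protocol*

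**What the plan says.** **Definition.** Section 6.1.2.1 states: "The first secondary endpoint is the number of new diagnoses of COPD and heart disease (CVD) in patients". The source is HCP reporting of the date and type of diagnosis, collected for up to 12 months. On multiplicity it says: "If multiple diagnoses are recorded, all will count towards the endpoint". In countries where a preliminary diagnosis is entered before testing so that medication can be prescribed, "the date of diagnosis will be validated by the HCP to ensure final clinical diagnosis date".

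**Analysis.** For the same endpoint, section 8.2.2 reports the frequency "and cumulative incidence of new (working) diagnosis of COPD and/or heart disease". The next bullet of 8.2.2, on usability and efficiency, lists "The distribution of working diagnosis outcomes from the BiaB box".

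**Who reports.** The Introduction says that "the application provides a report for the HCP as a guidance for the diagnosis in patients with breathlessness". Under section 6.3.3 the HCPs report the diagnosis at Visit 1 and every three months for up to a year.

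**Hypothesis.** Section 8.2.1 expects BiaB to increase new COPD and/or heart disease diagnoses.

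**The concern.** A working diagnosis and a final clinical diagnosis give different counts whenever the first is later withdrawn. One section points to the final diagnosis and the other admits the working one, so the protocol does not settle which patients are events.

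The choice may not be neutral between the periods. In the BiaB period every patient has the full set of tests apart from YEARS and D-dimer (section 5), and the HCP receives a report that suggests a diagnosis. That same HCP knows the period and reports the endpoint. If labels prompted by the box are recorded and later refuted, the protocol has no rule that takes them out again. The resulting error would lie in the direction of the stated hypothesis. A higher count could then mean better detection or more labelling, and the endpoint as worded in 8.2.2 could not tell them apart.

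**Working it through.** The protocol gives no expected rate, sample size or power for this endpoint, so there is no figure to reproduce. The check is a comparison of passages, followed by an illustration of scale.

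**Passages side by side**

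| Question | 6.1.2.1 | 8.2.2 |
|---|---|---|
| What counts? | New diagnoses | New diagnoses, with *working* in brackets |
| Preliminary diagnoses? | HCP validates the date, in some countries only | Not mentioned |
| Source? | HCP report | Not restated; *working diagnosis* also names the box output |
| Confirmation or removal if refuted? | None stated | None stated |

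The validation in 6.1.2.1 shows that the final diagnosis is the intended target. It covers only the date, applies only in some countries, and is done by the HCP.

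**Illustration of scale**

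Inputs from the protocol:
- 900 patients at 1:1 (section 3), so 450 per condition.
- Two-sided type I error 0.05 and intraclass correlation 0.03 (section 4.3, set for the primary endpoint and borrowed here).
- 20 patients per site.

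Assumed inputs, not in the documents:
- True incidence *p* of COPD or heart disease, equal in both conditions: 0.2, 0.3 or 0.4.
- Share *f* of patients without the disease who carry an unconfirmed label that is counted: *f_B* in BiaB and *f_U* in usual care.

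Expected false difference = (1 − p)(f_B − f_U).

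With f_U = 0, the observed BiaB proportion is q = p + (1 − p)f_B. With p̄ = (p + q)/2, the probability of declaring an increase is approximately

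Φ{ [q − p − 1.96·√(2p̄(1 − p̄)/n)] / √([p(1 − p) + q(1 − q)]/n) }.

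Two values of n are used. One is 450, with no clustering. The other is 450/1.57 = 286.6, with design effect 1 + 19 × 0.03 = 1.57. The second is a rough allowance for clustering, not the stepped-wedge model.

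| p | f_B | q | Extra patients per 450 | P, no clustering | P, design effect 1.57 |
|---|---|---|---|---|---|
| 0.2 | 2% | 0.216 | 7.2 | 0.086 | 0.068 |
| 0.3 | 2% | 0.314 | 6.3 | 0.066 | 0.055 |
| 0.4 | 2% | 0.412 | 5.4 | 0.056 | 0.048 |
| 0.2 | 5% | 0.240 | 18.0 | 0.304 | 0.210 |
| 0.3 | 5% | 0.335 | 15.75 | 0.202 | 0.144 |
| 0.4 | 5% | 0.430 | 13.5 | 0.148 | 0.109 |
| 0.2 | 10% | 0.280 | 36.0 | 0.803 | 0.612 |
| 0.3 | 10% | 0.370 | 31.5 | 0.605 | 0.427 |
| 0.4 | 10% | 0.460 | 27.0 | 0.443 | 0.305 |

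The nominal value in the direction of BiaB is 0.05/2 = 0.025.

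The result depends on the difference f_B − f_U. At p = 0.3 with f_B = 10% and f_U = 5%, the excess is 0.7 × 0.05 = 3.5 percentage points, or 15.75 of 450 patients. With f_B = f_U it is zero. If usual care produced more unconfirmed labels, the bias would run against BiaB.

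**The case against.** The strongest reply is that box output is not the endpoint. The source in 6.1.2.1 is the diagnosis reported by the HCP. Section 6.1.2.2 compares the advice of the box with the diagnosis the HCP reports, which makes sense only if the two can differ. Section 8.2.2 lists the box's working diagnoses separately, under usability. Working diagnoses in usual care count as well. All of this stands, and it rules out a stronger claim that a reader might infer: that a box label counts automatically, so that BiaB raises the count by construction.

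On that reading, with 30% true cases all found and an assumed box specificity of 80 to 90%, 450 × 0.7 × 0.10 = 31.5 to 450 × 0.7 × 0.20 = 63 false positives would be added to 450 × 0.3 = 135 true cases, an increase of 23 to 47%. This requires every false positive of the box to be adopted and none to occur in usual care. The documents support neither.

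A reader might also infer from "If required, post-bronchodilator spirometry can also be performed using the ALDS device after training of HCPs" that COPD may be diagnosed without spirometry in the BiaB period only. Section 5.1.1 sets no such rule, and no section requires spirometry for a COPD diagnosis in usual care.

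Two further points have weight. Section 4 seeks real-world heterogeneity, so a clinician-recorded diagnosis is a legitimate endpoint. Section 8 also calls itself a summary and leaves technical detail to a statistical analysis plan, which may hold derivation rules. Neither removes the conflict between two sections of the protocol on what counts.

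**Conclusion.** The point holds as an inconsistency with a plausible route to bias. Sections 6.1.2.1 and 8.2.2 do not agree on whether a working diagnosis is an event. If it is, diagnoses prompted by the BiaB report, adopted by an unblinded HCP and later refuted, stay in the count.

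The documents fix neither the size nor the direction of the net effect. It depends on how much more often unconfirmed labels are recorded and kept in the BiaB period than in usual care. In the illustration the effect is small at a 2% excess among non-cases, moderate at 5% (0.11 to 0.21 with the clustering allowance) and serious at 10% (0.31 to 0.61). These values rest on assumed incidence and labelling rates and on a crude design effect. The primary endpoint's sample size is not affected. A correction is worth making because this endpoint carries its own stated hypothesis and the change is cheap.

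**What to change.** 1. In section 8.2.2, delete the bracketed word *working*. In both 6.1.2.1 and 8.2.2, define the event identically for the two periods: a patient with a new HCP-reported clinical diagnosis of COPD or heart disease that still stands at the last HCP report, up to 12 months. Counting patients follows the opening of the 8.2.2 bullet; the number of diagnoses per patient can stay as a descriptive result.
2. Report working diagnoses separately and descriptively, with the proportion that still stand at 12 months.
3. As a sensitivity analysis, restrict the count to diagnoses supported by a test outside BiaB. Use the HCP-reported procedures of section 6.1.2.2, collected in both periods. Do not use the specialist questionnaire of section 6.3.4: its link is on the BiaB report, so ascertainment would be unequal. Such confirmation should not become the main definition, because the endpoint would then depend on testing and referral that BiaB may itself change.

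**Cost.** Wording, plus a derivation from the three-monthly HCP reports. If the HCP form does not show whether an earlier diagnosis still stands, one item is needed. Somewhat fewer events will be counted.

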8.3 Other study parameters

8.3.1 Qualitative: Interviews with healthcare professionals

Audio recordings of interviews will be transcribed and analysed with qualitative content analysis. Transcripts will be analysed at fragment levels using content analysis by the research team. Content analysis will be conducted with Dedoose or comparable software. Data will be coded and analysed by two researchers and consensus will be reached about potential discrepancies. Results will be systematically discussed with the Scientific Advisory Board.

9. ETHICAL, DATA PRIVACY, AND LEGAL ISSUES

9.1 Regulation statement

This study will be conducted in accordance with the principles of the declaration of Helsinki (version October 2013).

9.2 Informed consent

9.2.1 Informed consent procedure

The healthcare professional (HCP) will explain the nature of the study to the patient after he or she has expressed interest in participating. Patients or their legally authorized representative will receive either a digital or hard copy of the Patient Information Sheet and Informed Consent Form (ICF). Patients must be informed that their participation is voluntary, and they are free to refuse to participate and may withdraw their consent at any time and for any reason during the study without any consequences. Depending on the specific regulations in patient's country, the informed consent procedure may either be directly initiated or after the minimum consideration period. If applicable, before signing, the HCP will explain the study again. Patients can ask any questions they may have. Upon satisfactory clarification of all questions, patients will be given the option to sign the ICF. Signatures can be provided either on paper or digitally.

9.2.2 Paper-based consent

The patient and HCP will sign the ICF on paper at the site. Following the signing process, one ICF will be retained at the site in_accordance with Good Clinical Practice (GCP) standards, while the other will be provided to the patient.

9.2.3 Electronic Consent

Signing the ICF electronically will be facilitated through the eConsent module of the designated Electronic Data Capture (EDC) system. The patient and HCP will sign the ICF using the study tablet. The eConsent module will comply with 21 CFR Part 11 regulations for electronic signatures and will incorporate encryption measures. HCP's will undergo two-factor authentication prior to signing the ICF. Upon completion of the signing process, the patient will receive a digital copy of the signed ICF.

9.2.4. Electronic Data Capture System

The HCP will either conduct a usual care visit or, during the intervention period, perform the BiaB. Regardless of whether the ICF signature is electronic or paper-based, visits data will be collected in an EDC system.

The medical record must include a statement that informed consent was obtained for the BiaB study and the date it was obtained. If new information requires changes to the ICF, it should be assessed whether patients need to undergo re-consent. If re-consent is deemed necessary, it

must be done using the most up-to-date version of the ICF available during their participation in the study.

The ICF will contain a separate section detailing the storage and utilization of data gathering during the study, aimed at selecting and potentially inviting patients to participate in other research studies. Patients will be informed of their freedom to decline participation in this additional use of their data in the future and retain the right to withdraw consent at any time and for any reason without any consequences.

9.3 Benefits and risks assessment, group relatedness

The risks of participating in the BiaB study are negligible because the box only contains non-invasive tests. The diagnostic test which are included in the box are all validated and approved tests, adding no elevated risks to this one study visit, when compared to usual care. There might occur a minor inconvenience for the patient, because of the finger stick necessary for the NT-proBNP test.

The overall aim of the study is to test whether the use of the BiaB box reduces the time to clinical diagnosis, and consequently earlier treatment. The cost effectiveness assessments (including the quality of life questionnaire) will at the end conclude whether this has benefitted the patient, however the hypothesis is that it will.

Besides direct benefit for the specific patients that will be included in the study, we hope that raising awareness for breathlessness will indirectly influence the health of patients by inspiring the healthcare professionals in primary care.

10. ADMINISTRATIVE ASPECTS, MONITORING AND PUBLICATION

10.1 Handling and storage of data

Data collection in the BiaB-app

Data from the BiaB-app will be stored according to the medical information regulation by Lothar Medtech which complies with class IIa for continuous operation according to Annex IX of the Directive, also complies with the essential requirements according to EN ISO 13485:2016. medical devices - quality management systems - requirements for regulatory purposes.

Certification authority: TUEV SUED (CE0123) Certificate numbers: G10 102194 0002 Rev. 1

Data collection in electronic Data Capture system

All research data will be directly entered into an Electronic Data Capture system (EDC). The data collection software Castor or a comparable vendor will be used to ensure the adequate entry, management, and storage of the collected data. The selected EDC system will have an audit trail that enables the tracking of changes. Furthermore, the system enables the application of validation rules (e.g. halts when a value is incorrectly filled out e.g. an age value that is smaller than 18 or when a data field is accidently skipped). This will minimize errors and missing values on questionnaires. The selected EDC system should comply with all applicable laws and regulations, including ICH E6 Good Clinical Practice (GCP), 21 CFR Part 11, EU Annex 11, General Data Protection Regulation (GDPR), HIPAA (US), ISO 9001 and ISO 27001.

Data handling and storage will comply with the General Data Protection Regulation (GDRP). The investigator will ensure protection of patient's personal data in compliance with the Personal Data Protection Act and that all reports, publications, patient samples and any other study disclosures do not reveal the identity of the patient, except where required by laws. Patients are identified only by a patient identification number or site identification number to maintain patient confidentiality. All patient study records will be kept safely in an access- controlled area. Identification code lists linking patient names to patient identification numbers should preferably be stored separate from patient records. In case of data transfer, the sponsor or its representative will maintain high standards of confidentiality and protection of patient personal data. Clinical information will not be released without the written permission of the patient, except for monitoring by clinical quality assurance auditors or other authorized personnel appointed by the sponsor, by appropriate IRB members, and by inspectors from regulatory authorities.

